## Flow Chart (20 mg/kg b.w. dose group, single dose)

dose group, single	Day	Time relative to first drug administration (planned time [h:min])	Approx. time (actual time) [h:min]	Event and comment		PK plasma 	PD blood 	Plasma ADA 	Laboratory/ Urinalysis 	Body Temperature	Body Weight	12-lead ECG	ECG monitoring	Vital signs (BP, PR)	Query on adverse events, concomitant therapies 
1	-28 to -3			screening 				X				X		X	
2	-2	-48:00	8:00	ambulatory visit				X 							
	-1	-12:00	20:00	admission to trial site				X 							X
1	1	-2:00	6:30			X 	X 	X 	X 	X 		X 		X 	X 
		0:00	8:00	drug administration start of infusion										▲	
		0:30	8:30	▼ end of infusion 		X	X			X		X 		X	X 
		1:00	9:00							X		X 		X	X 
		1:30	9:30									X 		X	
		2:00	10:00	light breakfast 		X				X		X 	▼	X	
		2:30	10:30												
		3:00	11:00			X						X 		X	
		4:00	12:00	Lunch 		X			X 			X 		X	X 
		6:00	14:00							X		X 		X	
		8:00	16:00	snack (voluntary) 		X						X 		X	
		10:00	18:00	Dinner 											
		12:00	20:00			X				X		X 		X	X 
	2	24:00	8:00	Breakfast 		X			X 	X		X 		X	X 
		28:00	12:00	Lunch 											
		32:00	16:00	snack (voluntary) 						X		X 		X	
		34:00	18:00	Dinner 											X
3	48:00	8:00	Breakfast  discharge from trial site (confirmation of fitness  )		X							X 		X	X
4	72:00	8:00	ambulatory visit		X			X							X
5	96:00	8:00	ambulatory visit		X										X
8	168:00	8:00	ambulatory visit breakfast (voluntary)		X	X	X	X				X		X	X
15	336:00	8:00	ambulatory visit		X										X
22	504:00	8:00	ambulatory visit breakfast (voluntary)		X	X		X				X		X	X
29	672:00	8:00	ambulatory visit breakfast (voluntary)		X	X	X	X				X		X	X

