12. AEs and concomitant therapies will be recorded throughout the trial, but will be specifically asked for at the time points indicated in the [Flow Chart](#) above.
13. EOT (End of trial examination) includes physical examination, body weight, vital signs, ECG, safety laboratory, recording of AEs and concomitant therapies. EOT to be performed not before last PK and ADA sampling.
14. Safety laboratory is to be taken within three days prior to study drug administration and can be omitted, if the screening examination is performed between Day -5 to Day -3.
15. First measure after completion of infusion collection of PK and PD sample
16. In case plasma levels still exceed LOQ additional PK samples may be collected beyond Day 176.

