#### 4.1.4 Drug assignment and administration of doses for each subject

The treatments to be evaluated are outlined in [Table 4.1.4: 1](#) below. The dose volume for placebo corresponds to the dose volume of the respective dose level. For further details concerning timing see [Flow Chart](#). Start and time of the infusion will be recorded.

Detailed instructions for the dilution of the trial product, the preparation of the infusion solution, the volume to be administered and the infusion rate is provided in [Appendix 10.2](#). In all subjects the infusion solution will be intravenously administered over 30 minutes for dose group 3 mg/kg b.w. multiple dose and 6 mg/kg b.w. multiple dose and over 60 minutes for dose group 10 mg/kg b.w. multiple dose and 20 mg/kg b.w. single dose approximately between 8.00 h and 10.30 h of the respective study day. Multiple doses of 20 mg/kg b.w. will be administered over 90 minutes between 8.00 h and 12.00 h of the respective study day.

In case of safety concerns, e.g. due to infusion reactions, it is in the discretion of the investigator or his/her designee to adapt the infusion scheme, including but not limited slowing down the infusion rate, stopping of the infusion and provided no further safety concern exist restarting at a slower rate. Further based on █ medical judgment he/she will provide medications such as steroids, etc. as needed.

For administration of the infusion, an intravenous indwelling catheter is placed into an arm vein of the subject and will be kept patent with a saline infusion. A second indwelling catheter used for collection of blood samples will be placed on the contralateral arm.

The administration of the trial medication on all study days will be done under supervision of the investigating physician or a designee. The so-called four-eye principle (two-person rule)

should be applied for administration of trial medication and – if applicable – its preparation (e.g. reconstitution), if correct dosage cannot be ensured otherwise. For the purpose of drug accountability, the infusion set will be weighed before and after drug administration.

Table 4.1.4: 1 Preparation of infusion solution containing active drug

Dose group	Final dose of BI 655130 [mg/kg]	Concentration of Application solution in infusion bag	Infusion volume [mL]*/ Total dose [mg]
1	3	20 mg/mL	9 mL → 180 mg
2	6	20 mg/mL	18 mL → 360 mg
3	10	20 mg/mL	30 mL → 600 mg
4	20	20 mg/mL	60 mL → 1200 mg
5	20	20 mg/mL	60 mL → 1200 mg

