#### Preparation overview:

Dilution: 22.5 mL of BI 655130 Solution for Infusion 20 mg/mL + 67.5 mL 0.9% sodium chloride → 90 mL 5.0 mg/mL BI 655130 (in infusion bag)

- 1) Put a Mini-Spike on a bottle containing 500 mL 0.9% sodium chloride solution
- 2) Attach a 50 mL syringe to the Mini-Spike, withdraw 50 mL of the 0.9% sodium chloride Solution and disconnect the filled syringe. Close it with a Combi-Stopper.
- 3) Attach a 20 mL syringe to the Mini-Spike, withdraw 17.0 mL of the 0.9% sodium chloride solution and disconnect the filled syringe. Close it with a Combi-Stopper.
- 4) Attach a 1 ml syringe to the Mini-Spike, withdraw 0.5 mL of the sodium chloride solution and disconnect the filled syringe. Close it with a Combi-Stopper.
- 5) Put a Mini-Spike on each of two vials containing BI 655130 Solution for Infusion 20 mg/mL and connect one 20 mL syringe to the Mini-Spike.
- 6) Withdraw 7.5 mL of BI 655130 Solution for Infusion 20 mg/mL from each of the two so the total volume in the syringe is 15.0 mL (= 300 mg BI 655130).
- 7) Disconnect the syringe and lock the syringe with a Combi-Stopper.
- 8) Put a Mini-Spike on the third vial containing BI 655130 Solution for Infusion 20 mg/mL and connect one 10 mL syringe to the Mini-Spike.
- 9) withdraw 7.0 mL of BI 655130 Solution for Infusion 20 mg/mL from the vial (= 140 mg BI 655130)
- 10) Disconnect the syringe and lock the syringe with a Combi-Stopper.
- 11) Attach a 1 mL syringe to the Mini-Spike, withdraw 0.5 mL of BI 655130 Solution for Infusion 20mg/mL from the vial (= 10 mg BI 655130) and disconnect the filled syringe. Close it with a Combi-Stopper.
- 12) Lock the fill port of the empty infusion bag close to the bag. Open the injection port of the bag.
- 13) Remove the Combi-Stopper from the syringe obtained in step 6, attach an 18 G needle and transfer the complete contents of the syringe into the infusion bag via the injection port.
- 14) Disconnect the empty syringe from the needle and close the needle using a Combi-Stopper. Keep bag in an upright position to prevent leakage.

Proprietary confidential information © 2017 Boehringer Ingelheim International GmbH or one or more of its affiliated companies

- 15) Connect consecutively the second syringe containing BI 655130 Solution for Infusion (step 9) to the needle of the infusion bag containing BI 655130 Solution for Infusion 20 mg/mL (step 13) and transfer the content of the syringes completely into the infusion bag. Disconnect the empty syringe.

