**Preparation overview:**

Dilution: 45 mL of BI 655130 Solution for Infusion 20 mg/mL + 45 mL 0.9% sodium chloride → 90 mL 10.0 mg/mL BI 655130 (in infusion bag)

- 1) Put a Mini-Spike on a bottle containing 500 mL 0.9% sodium chloride solution
- 2) Attach a 50 mL syringe to the Mini-Spike, withdraw 45 mL of the 0.9% sodium chloride Solution and disconnect the filled syringe. Close it with a Combi-Stopper.
- 3) Put a Mini-Spike on each of the 6 vials containing BI 655130 Solution for Infusion 20 mg/mL and connect one 50 mL syringe to the Mini-Spike.
- 4) Withdraw 7.5 mL of BI 655130 Solution for Infusion 20 mg/mL from each of the 6 vials so the total volume in the syringe is 45.0 mL (= 900 mg BI 655130).
- 5) Disconnect the syringe and lock the syringe with a Combi-Stopper.
- 6) Lock the fill port of the empty infusion bag close to the bag. Open the injection port of the bag.
- 7) Remove the Combi-Stopper from the syringe obtained in step 4, attach an 18 G needle and transfer the complete contents of the syringe into the infusion bag via the injection port.
- 8) Disconnect the empty syringe from the needle and close the needle using a Combi-Stopper. Keep bag in an upright position to prevent leakage.
- 9) Connect the syringe containing 0.9% sodium chloride solution (step 2) to the needle of the infusion bag containing BI 655130 Solution for Infusion 20 mg/mL (step 8) and transfer the contents of the syringe completely into the infusion bag. Disconnect the empty syringe.
- 10) Remove the needle and mix solution in the bag by gently kneading and turning it.

**Preparation instructions for 10 mg/kg dose (drug concentration in infusion solution 20 mg/mL BI 655130):****Necessary Materials:****Drug Product:**

10 vials BI 655130 Solution for Infusion 20 mg/mL (correlates to 10 x 150 mg BI 655130)

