**Infusion Information:**

Dose (mg/kg)	In-line Filter Used?	Approximate Pre-flush Volume (mL)	Concentration of the ready to use i.v. bag BI 655130 (mg/mL)	Volume Delivered (mL/kg body weight)	Infusion Time (min)
3	Yes	30	5	0.6	Up to 240
6	Yes	15	10	0.6	Up to 240
10	Yes	15	20	0.5	Up to 240
20	Yes	15	20	1	Up to 240

After preparation, the solution for infusion may be stored at 2-8°C for up to 24 hours. After removal from 2-8°C storage or preparation, the solution must be administered within 60 minutes if stored at  $\leq 25^{\circ}\text{C}$ . Do not freeze.

Chemical and physical in-use stability has been demonstrated for 60 minutes at  $\leq 25^{\circ}\text{C}$ . In addition the time for infusion must not exceed 240 minutes at  $\leq 25^{\circ}\text{C}$ .

From a microbiological point of view the drug should be used immediately. If not used immediately, the in-use storage times and conditions prior to use are the responsibility of the user, and would normally not be longer than 24 hours at 2-8°C (36-46°F), unless preparation has taken place in controlled and validated aseptic conditions.

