5.4.2 Treatment compliance and treatment exposure

Treatment exposure is assessed by means of

- the total infused dose of BI 655130 [mg] per subject, the
- infused dose of BI 655130 [mg/kg body weight] per subject and infusion,
- the duration of infusion per subject and infusion, and
- the number of infusions per subject.

The total dose of BI 655130 [mg] received is calculated as the total infusion volume [mL], as documented on the eCRF, times the drug concentration in the infusion solution (which is 5 mg/mL for subjects in the 3 mg/kg dose group, 10 mg/mL for subjects in the 6 mg/kg dose group, and 20 mg/mL for subjects in the 10 mg/kg and 20 mg/kg dose groups). The dose of BI 655130 [mg/kg body weight] will be calculated as the total dose of BI 655130 received divided by the body weight [kg] of the patient on Day -2.

The duration of the infusion of BI 655130 [minutes] will be calculated as the end of the infusion date/time minus the start of the infusion date/time.

Treatment compliance will be assessed based on the actual number of infusions, duration of infusions and dose per infusion.

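### Table 4.1.4: 1 contradicts Appendix 10.2 and the SAP on the 3 and 6 mg/kg infusion bags, and the 20 mg/kg single-dose flow chart ends a 60-minute infusion at 0:30

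*Protocol*

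**What the plan says.** **Bag concentration and volume.** Table 4.1.4: 1 of the Protocol has a column headed "Concentration of Application solution in infusion bag". It reads 20 mg/mL in all five dose groups. For a 60 kg subject the table gives 9 mL (180 mg) at 3 mg/kg and 18 mL (360 mg) at 6 mg/kg.

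Appendix 10.2 dilutes these two doses. The 3 mg/kg preparation yields "90 mL 5.0 mg/mL BI 655130 (in infusion bag" and the 6 mg/kg preparation yields "90 mL 10.0 mg/mL BI 655130 (in infusion bag". Its Infusion Information table sets the delivered volume at 0.6 mL/kg for both. SAP 5.4.2 computes the dose received as recorded volume times concentration, "which is 5 mg/mL for subjects in the 3 mg/kg dose group, 10 mg/mL for subjects in the 6 mg/kg dose group". Section 4.1.4 itself refers to Appendix 10.2 for dilution, volume and rate.

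**End of infusion, 20 mg/kg single dose.** Section 4.1.4 gives the infusion "over 60 minutes for dose group 10 mg/kg b.w. multiple dose and 20 mg/kg b.w. single dose", and the synopsis and SAP Table 6.7.4: 1 also give 60 minutes. SAP Table 6.7.4: 2 puts end of infusion for this group at 1:00. The single-dose flow chart instead prints "end of infusion" on the 0:30 row (clock time 8:30), with the PK and PD marks on that row. The 1:00 row has no PK or PD mark, and the next PK sample is at 2:00. Footnote 15 to that chart reads "First measure after completion of infusion collection of PK and PD sample".

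**The concern.** The column in Table 4.1.4: 1 describes the bag, so 20 mg/mL cannot be read as vial strength. For groups 1 and 2 the protocol therefore holds two incompatible pairs of concentration and volume. The intended dose is safe only if both numbers come from the same place. Taking the table volume from the bag that the pharmacy is told to prepare underdoses the subject. Conversely, a dose actually prepared and given as the table describes would be under-reported by the SAP exposure formula, which applies 5 or 10 mg/mL to whatever volume was recorded.

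In the single-dose chart, site staff cannot follow both the 0:30 row and footnote 15, because a 60-minute infusion is not complete at 0:30. Each choice has a cost:

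- **Sample at 0:30.** The sample is mid-infusion, and Cmax, a secondary endpoint, is then read at 2:00. The SAP's 1:00 end-of-infusion time point for biomarkers has no scheduled sample.
- **Sample at completion (1:00).** The concentration carries the planned time 0:30. SAP 6.7.1 pairs PK and ECG by planned time and lists separate 0:30 and 1:00 ECGs for this group. The 1:00 concentration would be paired with the 0:30 ECG unless re-matched, and the 1:00 ECG would have no PK partner. The sample would also miss its nominal time by 30 minutes, against a tolerance of ±1 minute in section 6.1.

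**Working it through.** **Inputs.** From Protocol section 4.1.4: body weight 60 kg, 20 mg/mL, 9 mL and 18 mL. From Appendix 10.2: 22.5 mL drug plus 67.5 mL saline (3 mg/kg), 45 mL plus 45 mL (6 mg/kg), product at 20 mg/mL, delivery 0.6 mL/kg. From SAP 5.4.2: 5 and 10 mg/mL.

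**Step 1: reproduce each source.** Dose = volume × concentration.

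- Appendix bag concentrations: 22.5 × 20 / 90 = 5 mg/mL and 45 × 20 / 90 = 10 mg/mL.
- Appendix volume at 60 kg: 0.6 × 60 = 36 mL in both groups.

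| Combination (60 kg) | 3 mg/kg group | 6 mg/kg group |
|---|---|---|
| Table volume, table concentration | 9 × 20 = 180 mg | 18 × 20 = 360 mg |
| Appendix volume, appendix concentration | 36 × 5 = 180 mg | 36 × 10 = 360 mg |
| Table volume, appendix concentration | 9 × 5 = 45 mg | 18 × 10 = 180 mg |

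Both sources are internally correct and reach the same total dose. They differ 4-fold (3 mg/kg) and 2-fold (6 mg/kg) in concentration and, inversely, in volume.

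**Step 2: size of a mix-up.** 45 / 60 = 0.75 mg/kg, a quarter of 3 mg/kg. 180 / 60 = 3 mg/kg, half of 6 mg/kg. These do not depend on body weight, because the table volumes are 0.15 and 0.30 mL/kg: 0.15 × 5 = 0.75 and 0.30 × 10 = 3. The same products are what the SAP formula would report for a dose truly given as the table describes.

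**Step 3: the other rows.** At 10 mg/kg the table has 30 mL and the appendix 0.5 × 60 = 30 mL. At 20 mg/kg the table has 60 mL and the appendix 1 × 60 = 60 mL. All are at 20 mg/mL, so only groups 1 and 2 conflict.

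**Step 4: the single-dose sample.** At a constant rate, the amount infused by 0:30 is 20 × 30 / 60 = 10 mg/kg. If Cmax is then read at 2:00, one hour after the end of infusion, the shortfall is 1 − 2^(−1/h) for an initial half-life of h hours. The documents give no distribution half-life, so h is an assumption:

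| Assumed h (hours) | Shortfall in Cmax |
|---|---|
| 6 | 10.9% |
| 12 | 5.6% |
| 24 | 2.8% |
| 48 | 1.4% |

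**Step 5: could the 0:30 row be an artefact of reading the PDF?** The end-of-infusion label and both sample marks sit together on the 0:30 row. The chart's ECG marks at 0:30, 1:00, 1:30 and 2:00 agree with SAP Table 6.7.1: 1. The 10 mg/kg chart, also a 60-minute infusion, shows the label and samples at 1:00. A shifted row is therefore unlikely.

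**The case against.** **On the table.** Section 4.1.4 makes Appendix 10.2 the governing instruction, and the appendix is complete in itself. Underdosing needs someone to prepare the appendix bag, ignore the appendix's own volume column, and take the volume from a 60 kg illustration. Misreporting needs the opposite departure, an undiluted bag. The two-person rule and the weighing of the infusion set lower the risk further, and the SAP already holds the right concentrations. All this stands as a limit on likelihood. It does not make the two rows correct. It is also fair to say that nothing is miscalculated: this is a conflict between sources.

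**On the flow chart.** Footnote 15 ties the sample to completion, and actual sampling times are used for PK parameters, so if staff sample at 1:00, Cmax itself is unaffected. SAP 6.7.1 allows a value to be matched to another time point no later than the report planning or database lock meeting. Single-dose Cmax also carries limited weight: SAP 7.5.2 excludes this group from dose proportionality and SAP section 4 drops the relative bioavailability analysis. It does still feed descriptive statistics and a prediction point in the exploratory concentration-QTc model. These points stand, but they repair the data after the event. Section 4.1.4 sends staff to the Flow Chart for timing, so the 0:30 row is an operative instruction. SAP Table 6.7.4: 2 does give 1:00, but it covers vital signs, body temperature, ECG and biomarkers, not plasma concentrations.

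**On the size.** The 11% figure is the extreme of an assumed range. The only half-life in the documents, about 4 weeks (in the rationale for Amendment 1), would give 1 − 2^(−1/672), about 0.1%. It was quoted to set the length of follow-up and says little about decline in the first hour after an infusion.

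**Conclusion.** Both conflicts are present in the current text, and both items are wrong as written. Section 4.1.4 defers to Appendix 10.2, and SAP 5.4.2 agrees with the appendix on concentration, so the table rows are the items out of date. A mix-up would give 0.75 instead of 3 mg/kg, or 3 instead of 6 mg/kg. If each source is followed alone, the dose is right.

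For the single-dose group, the chart taken literally puts the end-of-infusion sample at half the dose and leaves the SAP's 1:00 biomarker time point unsampled. The resulting understatement of Cmax is about 1% to 11%, conditional on the assumed 48 to 6 h initial half-life and a constant infusion rate. If staff follow footnote 15, the harm is confined to analyses by planned time, mainly the PK and ECG pairing.

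The safeguards make serious harm unlikely, but dosing volumes and sampling times are instructions that people act on, so both should be corrected.

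**What to change.** In Table 4.1.4: 1, change the group 1 row to 5 mg/mL and 36 mL (180 mg) and the group 2 row to 10 mg/mL and 36 mL (360 mg). Leave groups 3 to 5 as they are.

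In the 20 mg/kg single-dose flow chart, move the end-of-infusion marker with its PK and PD marks from 0:30 to 1:00, and keep the ECGs at both times. The chart then agrees with footnote 15, section 4.1.4 and SAP Tables 6.7.4: 1 and 6.7.4: 2.

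The cost is four table cells and one flow-chart change in a protocol amendment. The SAP needs no change. For subjects already dosed, check the recorded infusion volumes and actual sampling times at the planned report planning or database lock meeting, and re-match PK and ECG pairs where needed.

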#### 4.1.5 Blinding and procedures for unblinding

##### 4.1.5.1 Blinding

For the MRD part, the trial is designed double-blind with regard to the subjects and the investigators (as well as the research staff at the trial site) in order to eliminate observer or performance bias. This means avoiding systematic differences in assessments regarding the subject's treatment (active or placebo).

The administration of the 20 mg single dose (active or placebo) will be single-blind (to assure single-blind conditions, subjects will not be informed about treatment assignment on the study days, i.e. subjects will not be aware that the second cohort of each dose level will only receive active treatment).

According to the rising dose design, the current dose level will be known to subjects and investigators.

At the trial site, access to the randomisation schedule is restricted to unblinded pharmacists, pharmacy staff members or staff who will reconstitute the drug solution. Access to the codes will be controlled and documented by a signed confidentiality statement, which will be stored

in the TMF. Persons directly involved in the clinical conduct of the trial will not have access to the treatment allocation prior to database lock.

Within the ECG laboratory, the staff involved with interval measurements and assessments will be blinded for the MRD part and unblinded for the SRD part with respect to the treatment and also with regard to the recording date and time as well as the time points of the ECGs. The interval measurements for a given subject will be performed in a random and blinded sequence by a single technician. No more than two different blinded readers will evaluate the ECGs of the study.

In addition, the trial bioanalyst will request the randomisation codes prior to official unblinding to perform the interim / preliminary PK analysis. He or she will confirm in writing that the codes will be treated confidentially.

Regarding the sponsor, the database of this trial will be handled open-label, meaning that the trial functions of the sponsor are unblinded (including clinical monitor, data manager, statistician, bioanalyst, pharmacokineticist, pharmacometrist, drug metabolism scientist as well as dedicated CRO personnel). The objective of the trial is not expected to be affected.

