Abnormal findings will be reported as AEs (during the trial) or baseline conditions (at screening) if judged clinically relevant by the investigator. Any ECG abnormalities will be monitored carefully and, if necessary, the subject will be removed from the trial and will receive the appropriate medical treatment.

In addition, a centralised evaluation of all 12-lead ECGs recorded from baseline up to 48 h after each dosing will be performed by an independent ECG laboratory. For this analysis, RR and QTall intervals will be determined semi-automatically, whereas PR and QRS intervals are determined by a validated GE 12-SL-algorithm or equivalent by the ECG core lab. Other parameters (e.g. cardiac axis) are determined by a validated GE 12-SL-algorithm or equivalent but do not undergo semi-automatic evaluation. For each QT interval, the RR interval preceding the QT will be measured to calculate the respective frequency corrected QTc intervals 'QTcF' according to Fridericia's formula ( $QTcF = QT / RR^{1/3}$ ) and 'QTcB' according to Bazett's formula ( $QTcB = QT / RR^{1/2}$ ). The QTcF correction will be used for evaluation and reporting. Abnormalities detected during centralised ECG evaluation will not necessarily qualify as AE. All interval measurements in one subject will be performed on the same lead. The intervals will be measured from four cardiac cycles (beats) in lead II. If lead II shows a flat T wave or is not measurable for any reason, lead V5 will be used, or if that lead is not measurable, then lead I will be used. The lead actually used will be reported in the CTR.

Within the ECG laboratory, the staff involved with ECG interval measurements and assessments will be blinded with regard to treatment, date and time as well as time points of the ECG measurements. The interval measurements for a given subject will be performed in random sequence by a single technician. No more than two different blinded readers will evaluate all ECGs of the study. For quality assurance and control of the measurements, all ECGs of a subject will be subsequently reviewed by the ECG technician supervisor or his/her designee with respect to the overall variance of the measured intervals, in order to detect accidentally switching of leads and/or false subject assignments of the ECGs. After the quality control the fiducial point markings will be reviewed by the cardiologist assigned to the study.

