If there is no non-linearity or delayed effect seen, the relationship between BI 655130 plasma concentrations and QTcN changes from baseline will be investigated in an exploratory manner using a random coefficient model approach to estimate the QTcN change from baseline and its 90% confidence interval at the geometric mean of the C_{max} for each dose (multiple dose groups as well as single dose group). Additionally, the estimated slope with its 90% confidence interval will be provided. The used random coefficient model is based on Garnett et al. 2016 [R17-0553] ([10](#)):

```
PROC MIXED DATA=myDATA METHOD=REML;
CLASS subject active(ref=FIRST) time;
MODEL ECGep = conc active time / NOINT CL ALPHA=0.1 ALPHAP=0.1 DDFM=KR
    OUTPREDM=pred;
RANDOM INT conc / TYPE=UN SUBJECT=subject;
ESTIMATE 'Pred. value at conc. xx.xx' conc xx.xx active 1 -1 / CL
    ALPHA=0.1;
ESTIMATE 'Slope estimate' conc 1 / CL ALPHA=0.1;
RUN;
```

Here "ECGep" is the QTcN change from baseline, "active" is a dummy 0/1 variable indicating the active treatment (1=active, 0=placebo), "conc" is the corresponding plasma concentration value of the drug, and "xx.xx" is the given concentration value (i.e. the value of the geometric mean C_{max} of a given dose group). The class variable "time" is the time relative to the most recent infusion; here, measurements at time points at the end of infusion will not enter the model with the planned time, but only by means of the time points defined in [Table 6.7: 3](#). The "TYPE=UN" option causes the two specified random coefficients to have a bivariate normal distribution. In case of convergence problems see [Section 9.2](#) for possible improvements (option "TYPE=FA0(2)" may also be used as a potential solution, it requests a G matrix estimate that is constrained to be nonnegative definite). If the note "estimated G matrix is not positive definite" occurs in the SAS log file, the random slope "conc" might be removed from the "RANDOM" statement. When the plasma concentrations are not normally distributed, the exposure-response model can be applied to $\log(\text{conc})$ instead of the raw concentration.

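### The protocol unblinds the ECG readers for the single-dose part in one clause of 4.1.5.1 and requires blinded reading of all ECGs elsewhere; the two must be reconciled

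*Protocol*

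**What the plan says.** Four statements in the current protocol text bear on reader blinding.

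- Section 4.1.5.1: ECG laboratory staff "will be blinded for the MRD part and unblinded for the SRD part with respect to the treatment". SRD here means the single-dose part. The sentence continues "and also with regard to the recording date and time as well as the time points of the ECGs".
- Section 4.1.5.1, next sentence: "The interval measurements for a given subject will be performed in a random and blinded sequence by a single technician".
- Section 4.1.5.1, the sentence after that: "No more than two different blinded readers will evaluate the ECGs of the study".
- Section 5.2.4.1: the same staff "will be blinded with regard to treatment, date and time as well as time points of the ECG measurements".

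The last three make no exception for the single-dose part. Section 5.2.4.1 also says that "RR and QTall intervals will be determined semi-automatically", whereas PR and QRS come from an algorithm.

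The SAP is silent on reader blinding. It uses the single-dose ECGs in three ways:

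- Descriptive and categorical ECG results by treatment group (5.3.2, 7.8.4).
- The exposure-response model, which predicts at the geometric mean Cmax "for each dose (multiple dose groups as well as single dose group)" (7.8.4).
- The common QTcN correction slope, estimated from baseline and placebo ECGs of the whole treated set (9.1).

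**The concern.** A laboratory cannot follow all four statements. One that follows the first sentence reads dose group 4 unblinded; one that follows 5.2.4.1 does not. Neither document tells the analyst which happened.

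QT and RR are the intervals in which human judgement enters, and they are the ones carried into QTc. A reader who knows the treatment and the time point knows which recordings are the predose baseline and which are post-dose on active drug, so change from baseline is exposed. Section 4.1.5.1 itself names elimination of observer bias as the purpose of blinding. The stated ground for the single-blind label is that subjects are not told their treatment, and this alone does not require an external laboratory to know it.

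At stake are the single-dose group's QTc changes, categories and notable findings. To a smaller extent so are the exposure-response model, which has no term for dosing part, and the QTcN slope.

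**Working it through.** **1. Consistency of the text.** For the single-dose part:

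| Place | Treatment | Date, time, time point |
|---|---|---|
| 4.1.5.1, staff sentence | unblinded | unblinded, read literally |
| 4.1.5.1, reading sequence | not stated | random and blinded sequence |
| 4.1.5.1, readers | blinded readers | not stated separately |
| 5.2.4.1 | blinded | blinded |

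Three statements point to blinding and one against it. All are current text.

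**2. How much data is exposed.** Inputs are the group sizes in Protocol 3.1 (four multiple-dose groups and one single-dose group, each 6 active and 2 placebo), the time points in SAP Table 6.7.1: 1, triple ECGs, and the PK times in the flow charts.

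- Central time points per subject: 13 single-dose (predose plus 12); 7 per dose x 4 doses = 28 multiple-dose.
- Central ECGs: 13 x 3 x 8 = 312 single-dose; 28 x 3 x 32 = 2688 multiple-dose. Share: 312/3000 = 10.4%.
- Active on-treatment ECG-concentration pairs: 8 x 6 = 48 single-dose, assuming one end-of-infusion pair; (3 + 3 x 4) x 24 = 360 multiple-dose. Share: 48/408 = 11.8%.
- Single ECGs for the QTcN slope: single-dose 8 x 3 + 2 x 12 x 3 = 96; multiple-dose 32 x 3 + 8 x 27 x 3 = 744. Share: 96/840 = 11.4%.
- Central readings at 3, 4, 8 and 32 h exist only in the single-dose group.

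**3. Illustrative size.** The documents give no figure for reader bias, so the shift is an assumption: 2 or 5 ms, post-dose only, in the six single-dose active subjects.

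- That group's mean change from baseline moves by the whole assumed shift. This restates the input.
- Pooled active mean, weighted by observation: 2 x 48/408 = 0.24 ms and 5 x 48/408 = 0.59 ms. Weighted by subject: 2 x 6/30 = 0.4 ms and 5 x 6/30 = 1.0 ms.
- SAP model prediction at single-dose Cmax: the fixed effects of the SAP model (concentration, active, time) were fitted by generalised least squares. The profile was dose-proportional with a 4-week half-life (the figure in the rationale for protocol amendment 1). Assumed SDs were 5 ms between subjects and 7 ms residual. The prediction moves by 0.37 and 0.92 ms. With SDs of 3 to 8 ms and 5 to 10 ms, the ranges are 0.31 to 0.39 ms and 0.77 to 0.98 ms. These fits omit the SAP's random concentration slope; adding a modest one left the result at the same order.

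The assumed shift does not enter the QTcN slope, which uses only baseline and placebo ECGs. The slope is exposed only if those readings were themselves affected.

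**The case against.** **A drafting slip is at least as likely as a decision to unblind.** This stands. A reader might infer that the sponsor chose to read the single-dose ECGs unblinded, or that this was done. The documents support only that it could be done under one clause.

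**A reading difference could be examined afterwards.** A reader might infer that a bias could never be told apart from a drug effect. The documents do not support that. The ECGs are digital (3.1.1, 5.2.4.1) and can be re-read, and the model can be refitted without the single-dose group. The multiple-dose 20 mg/kg group gives blindly read Day 1 ECGs at the same mg/kg dose, although its planned infusion lasts 90 rather than 60 minutes. Section 5.2.4.1 also adds supervisor review and a cardiologist's review of the markings.

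**The mechanism is narrow.** A constant shift within a subject cancels in change from baseline; only a predose to post-dose difference survives. This largely stands, but the literal clause discloses time points as well as treatment, and the new-onset categories use absolute thresholds.

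**Pooling is limited.** It might seem that all QTc results mix the two parts. SAP 6.1 keeps the single-dose active and placebo groups separate in tables. Mixing occurs in the exposure-response model and the QTcN slope.

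**Absence of benefit is not shown.** No reason for unblinding is visible, but section 2.3, to which 3.1 refers for the single-dose cohorts, is not in the public text. That unblinding serves no purpose would be a judgement, not a finding.

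**Consequences are modest.** The primary endpoint is subjects with drug-related AEs, and no confirmatory testing is planned. Cardiac safety during the trial uses machine or investigator values; central results overrule them only in doubtful cases sent ahead. This stands.

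**Conclusion.** The contradiction is real and unresolved in both documents. If the unblinding clause were followed, about 10% of the central ECGs and about 12% of the active ECG-concentration pairs would be open to reader bias. The main effect would fall on the single-dose group's own change-from-baseline and categorical QTc results. The exploratory model and QTcN slope would be affected less, and the primary endpoint not at all.

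The figure of roughly 0.3 to 1.0 ms at single-dose Cmax is illustrative. It rests on an assumed post-dose shift of 2 to 5 ms confined to active subjects, on assumed SDs and on a simple concentration profile. It is not evidence that any bias occurred. The point deserves action because the correction is cheap and because, as written, nobody can tell how these ECGs were to be read.

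**What to change.** In Protocol 4.1.5.1, delete the part of the staff sentence that unblinds readers for the single-dose part. That section and 5.2.4.1 should then both blind ECG laboratory staff to treatment, date, time and time point in both parts. Send the laboratory no allocation data. Applied before reading, this costs one clause and no extra readings.

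The SAP is dated 07-SEP-17 and describes the planned treatments in the past tense, so some reading may already be done. If single-dose ECGs were read unblinded, say so in the SAP and the report, and run the exposure-response model with and without the single-dose group. That costs one sensitivity analysis for each response (QTcN, QTcF, QT and HR). A blinded re-read of the digital ECGs is optional and has a real cost, up to 312 recordings.
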